Efficacy will be assessed among all subjects who were eligible, randomized, and received at least one dose of study drug, classified according to the treatment actually received. Secondary tests of efficacy will assess subjects who were eligible, randomized, and judged compliant with treatment and follow-up as classified prior to breaking the blind. Serial assessments of average daily hours of OFF time as recorded in the Patient Motor Diary over the two days prior to each visit will be using mixed model for repeated measures (MMRM). The model will include fixed terms for treatment, visit, treatment x visit interaction and baseline measurement with subject-level unstructured covariance among repeated measurements. Other covariance structures may be used in case the model do not converge using unstructured covariance structure. Additional covariates may be included based on review prior to breaking the blind. The primary estimand of efficacy for each active dose vs. placebo will be the treatment-dependent difference in change from baseline to Day 27 and will be tested using linear contrasts of least-square means. Each comparison will test for significance at one-tailed p < 0.1 to control the overall type 1 error rate at 20% based on Dunnett's method for comparing two treatments to the same control. Additional contrasts will be used to test for a dose-dependent effect of treatment and to estimate dosage-dependent differences in change from baseline at all other visits. Additional and exploratory efficacy endpoints will be analyzed in the same model and using the same estimands. Subgroup analyses will assess the influence of selected demographic and disease-related characteristics.

PK Measures:

Concentrations of CVN424 in plasma will be summarized by dose level and by gender (if possible) over each scheduled sampling time using descriptive statistics. Individual plasma concentration data versus time will be presented in a data listing. PK parameters of CVN424 will be summarized by dose and by gender (if possible) using descriptive statistics.

Sample Size Justification:

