The safety and tolerability of single- and repeated (7 daily) administration of CVN424, including doses higher than in the present study, were previously demonstrated in a study with 64 healthy volunteers (NCT03657030). The target sample size of 45 subjects per treatment arm (total N=135) is considered to be sufficient for the preliminary evaluation of CVN424 safety, tolerability and efficacy in a PD population. The study will have 90% power to detect at least one instance of any TEAE with an expected incidence of 0.10 per participant exposed at a given dosage of CVN424.

When the true effect of both dosages is zero, the study will have an 80% probability of declaring neither dosage of CVN424 significantly better than placebo at reducing OFF time based on the one-tailed p < 0.1 criterion, allowing 20% non-evaluable (e.g., loss to follow-up, incomplete data) and assuming a standard deviation (SD) of 3 h for the change in OFF time from baseline

Study No. CVN424-201 Page 15 of 73

Protocol v. 4.0 14 July 2021

to 27 days. When the true effect of a dosage is a reduction in average OFF time of at least 1.5 h, the study will have an 80% probability of declaring at least one dosage of CVN424 significant based on the one-tailed p < 0.1 criterion. By this construction, the study has 80% power to detect whether CVN424 does not reduce OFF time and 80% power to detect whether CVN424 at one or both of the two dosages tested reduces OFF time by at least 1.5 h.

Study No. CVN424-201 Page 16 of 73

Protocol v. 4.0 14 July 2021

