6.0 STUDY DESIGN AND DESCRIPTION

6.1 Study Design

This is a phase 2, randomized, double-blind, placebo-controlled, multicenter study of two dose levels of oral CVN424 (low-dose 50 mg, high-dose 150 mg) in Parkinson's disease (PD) patients with motor fluctuations. The overall study design is depicted in Figure 1.

Figure 1. Schematic design of study

Approximately 135 subjects with Parkinson's disease will be enrolled. Following baseline safety and efficacy assessments, subjects will be randomized in a 1:1:1 ratio into one of 3 study arms to receive low-dose CVN424, high-dose CVN424 or matching placebo. The planned low-dose and high-dose levels will be 50 and 150 mg CVN424 per day, respectively, as shown in Table 3.

Subjects not randomized to placebo will initiate treatment with 50 mg CVN424 on Day 1. Thereafter, the low-dose arm will continue to receive 50 mg per day, while the high-dose cohort will increase their dosage to 150 mg CVN424 per day beginning on Day 8 ±2 days and continuing thereafter. This step-wise increase is intended to limit the changes that the first dose of CVN424 may elicit in vital signs (notably, increased temperature and heart rate, which were dose-dependent and not clinically significant in a healthy volunteer study). Investigator or their delegate will manage incident AEs according to their medical judgment.

Study drug supply will be dispensed (as suspension in amber colored bottles) on Day 1 and at subsequent weekly study visits. Study drug will be self-administered each morning on an outpatient basis as an oral suspension. Dosing on Day 1, Day 8 and Day 22 visits will be observed at the study site by Investigator or their delegate. For Visit Days 8 and 22, dosing of study drug (but not subjects' other medications) will be deferred until after collection of a blood sample for determination of the study drug "trough" concentration.

Study No. CVN424-201 Page 23 of 73

Protocol v. 4.0 14 July 2021

Following dosing on days 1 and 8, subjects will remain on site until at least 3 h after dosing for safety and PK assessments. Investigator or their delegate will manage any incident AEs.

The study visit schedule is summarized in Table 1. Follow-up assessments will occur approximately 7 days after the final (Day 27 or 28) dose. A summary of activities scheduled at each study visit is included in Section 9.3. A Schedule of Study Procedures is listed in Appendix A.

Table 1 Subject Visit Schedule

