12.1.5 Efficacy Analysis

Serial assessments of average daily hours of OFF time as recorded in the Patient Motor Diary over the two days prior to each visit will be analyzed using mixed model for repeated measures (MMRM). The model will include fixed terms for treatment, visit, treatment x visit interaction and baseline measurement with subject-level unstructured covariance among repeated measurements. Other covariance structures may be used in case the model does not converge using unstructured

Study No. CVN424-201 Page 60 of 73

Protocol v. 4.0 14 July 2021

covariance structure. Additional covariates may be included based on review prior to breaking the blind. Two co-primary estimands of efficacy will estimate treatment-dependent difference in change from baseline to Day 27, one for each active dose vs. placebo, and will be tested using linear contrasts of least-square means. Each co-primary comparison will test for significance at one-tailed p < 0.1 to control the overall type 1 error rate at 20% based on Dunnett's method for comparing two treatments to the same control. Additional contrasts will be used to test for a dose-dependent effect of treatment and to estimate dosage-dependent differences in change from baseline at all other visits. Additional and exploratory efficacy endpoints will be analyzed in the same model and using the same estimands.

Responder analysis will ascertain the incidence of clinically significant improvement.

Subgroup analyses will ascertain the potential impact on efficacy of subgroup variables reflecting various demographic and disease-related characteristics.

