12.2 Interim Analysis and Criteria for Early Termination

A futility analysis may be conducted once at least 50 patients have completed their Day 27 assessments. The focus of this unblinded analysis will be to assess the change from baseline in 2-day average OFF time at Day 27 as recorded in the Patient Motor Diary. Analysis of safety events and additional endpoints may be included. The analysis will be conducted by a biostatistician of the CRO who is not otherwise involved with the conduct of the study. Investigators, their study staff, patients, CRO team members, and the Sponsor will remain blinded. The outcomes of this analysis will include a recommendation to the Sponsor to:

- 1. Continue the study as planned; or
- 2. Discontinue randomization into one active treatment arm because of futility; or
- 3. Discontinue the study because of futility on both active treatment arms

The futility analysis will be described in the SAP.

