12.3 Determination of Sample Size

The safety and tolerability of single- and repeated (7 daily) administration of CVN424, including doses higher than in the present study, were previously demonstrated in a study with 64 healthy volunteers. The target sample size of 45 subjects per treatment arm (total N=135) is considered to be sufficient for the preliminary evaluation of CVN424 safety, tolerability, and efficacy in a PD population. The study will have 90% power to detect at least one instance of any TEAE with an expected incidence of 0.10 per participant exposed at a given dosage of CVN424.

When the true effect of both dosages is zero, the study will have an 80% probability of declaring neither dosage of CVN424 significantly better than placebo at reducing OFF time based on the one-tailed p < 0.1 criterion, allowing 20% non-evaluable (e.g., loss to follow-up, incomplete data) and assuming a SD of 3 h for the change in OFF time from baseline to 27 days. When the true effect of a dosage is a reduction in average OFF time of at least 1.5 h, the study will have an 80% probability of declaring that dosage of CVN424 significant based on the one-tailed p < 0.1 criterion. By this construction, the study has 80% power to detect whether CVN424 does not reduce OFF time and

Study No. CVN424-201 Page 61 of 73

Protocol v. 4.0 14 July 2021

80% power to detect whether CVN424 at one or both of the two dosages tested reduces OFF time by at least 1.5 h.

Study No. CVN424-201 Page 62 of 73

Protocol v. 4.0 14 July 2021

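### Testing each dose at one-tailed p < 0.1 gives a familywise error of about 16.7%, not the 20% credited to Dunnett's method; the 80% figures and Table 3's 40 per arm also need correcting

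*Combined protocol and SAP*

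**What the plan says.** Section 12.1.5 names two co-primary efficacy estimands, the difference from placebo in change in OFF time at Day 27 for each dose. Each is tested for "significance at one-tailed p < 0.1 to control the overall type 1 error rate at 20% based on Dunnett's method". The efficacy paragraph of the synopsis (Section 2.0) gives the same rule and the same 20%. Under Section 6.1, "subjects will be randomized in a 1:1:1 ratio into one of 3 study arms".

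Section 12.3 and the synopsis turn the 20% into an operating characteristic. When both true effects are zero, "the study will have an 80% probability of declaring neither dosage of CVN424 significantly better than placebo". For a true reduction of 1.5 h the two places differ:

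- Section 12.3 claims an "80% probability of declaring that dosage of CVN424 significant based on the one-tailed p < 0.1 criterion".
- The synopsis claims an "80% probability of declaring at least one dosage of CVN424 significant based on the one-tailed p < 0.1 criterion".

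Both close with the same summary: "By this construction, the study has 80% power to detect whether CVN424 does not reduce OFF time", paired with 80% power for a 1.5 h reduction at one or both doses.

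Section 12.3 and the synopsis give 45 subjects per arm (135 in total), and Section 6.1 gives approximately 135. Table 3 in Section 8.1.3 lists 40 in each of the three arms.

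**The concern.** The per-comparison threshold, the named method and the overall error rate do not fit together. Dunnett's method exists to use the correlation that a shared control creates. Once that correlation is used, two tests at 0.10 cannot have a joint error of 20%; doubling 0.10 ignores it. The same figure is then carried over as a point probability of 80% for a correct null conclusion.

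Three related statements are also loose. The 80% power is defined in two ways. The probability of not rejecting a true null is called power. The sample size in Table 3 is not the one on which the power rests.

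At stake is whether the SAP and study report describe the OFF-time comparisons correctly. If the text stands, the error rate and the null probability will be about 3 points off and credited to a method that does not give them. A reader also cannot tell which power quantity the study was sized for.

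**Working it through.** **Inputs.** One-tailed 0.10 per dose (12.1.5); 1:1:1 allocation (6.1); SD 3 h, effect 1.5 h, 20% non-evaluable, 45 per arm (12.3); 40 per arm (Table 3).

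**1. The plan's 20%.** The Bonferroni sum is 2 x 0.10 = 0.20, and 1 - 0.20 = 0.80. This reproduces both the 20% and the 80% for declaring neither dose.

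**2. The Dunnett figure.** With n per arm, each contrast has variance 2σ²/n and the two share the placebo variance σ²/n, so their correlation is (σ²/n)/(2σ²/n) = 0.5. The one-tailed critical value is z = 1.2816.

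- Normal: familywise error = 1 - P(Z1 < 1.2816, Z2 < 1.2816) = 0.1676, so P(neither) = 0.832.
- Bivariate t with 3 x 36 - 3 = 105 df, critical t = 1.2897: familywise error 0.1674, P(neither) = 0.833.
- A simulation of 1,000,000 trials with 36 per arm gives 16.7%.

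**3. Can another reading give 20%?**

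| Reading | Familywise error |
|---|---|
| Correlation 0.4 | 17.3% |
| Correlation 0.6 | 16.1% |
| Independent tests, 1 - 0.9² | 19.0% |
| p < 0.1 taken as a Dunnett-adjusted p-value | 10% (nominal 0.057 per dose) |
| Bonferroni sum | 20% |

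A Dunnett test with a true 20% familywise error has critical z = 1.168, a one-tailed threshold of about 0.121 per dose.

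**4. Per-dose power.** Power = Φ(δ/SE - 1.2816), with SE = 3 x √(2/n).

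- 45 per arm: 45 x 0.8 = 36 evaluable, SE = 0.7071, δ/SE = 2.1213, power = Φ(0.8397) = 79.9%. This reproduces the 80%.
- 40 per arm: 40 x 0.8 = 32 evaluable, SE = 0.75, δ/SE = 2.0, power = Φ(0.7184) = 76.4%.

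**5. Power for at least one dose.** Power = 1 - P(Z1 < 1.2816 - d1, Z2 < 1.2816 - d2), correlation 0.5, where d is δ/SE for a dose that works and 0 for one that does not.

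| | One dose works | Both work |
|---|---|---|
| 45 per arm (36 evaluable) | 80.2% | 91.3% |
| 40 per arm (32 evaluable) | 76.7% | 88.9% |

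**6. A near-coincidence.** At the 0.121 threshold, 32 evaluable per arm gives Φ(2.0 - 1.1684) = 79.7%, and 36 gives Φ(2.1213 - 1.1684) = 83.0%. So 45 per arm with p < 0.10, and 40 per arm with a true 20% Dunnett threshold, both give about 80%. The documents do not say how the mismatch arose, and this does not show it. It is a reason to reconcile the threshold, the error rate and Table 3 together.

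**The case against.** The strongest reply is that controlling an error rate at 20% means not exceeding it, and 16.7% does not. That stands: the claim is true as a bound, the error is on the safe side and the decision rule is sound. OFF time is also a secondary endpoint (Section 5.2.2); the primary endpoint is drug-related treatment-emergent adverse events. What this does not rescue is the attribution to Dunnett, or the 80% for declaring neither dose, which is given as a probability and not as a minimum.

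On power, the synopsis conditions on the true effect of a single dosage. If only one dose works, at-least-one power is 80.2%, so its figure is right in that case and understated if both work. This part is a mismatch of definitions more than a wrong number. Calling a null probability power is likewise mainly terminology, since the paragraph has just defined the quantity.

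On Table 3, every other statement of the sample size says 45 per arm or about 135, and Section 6.1 cites the table for dose levels. The 76.4% applies only if Table 3 governed enrolment, which nothing suggests. It is still a direct contradiction in the current text.

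Finally, the sponsor might have meant a true 20% Dunnett test. That cannot be ruled out, but one-tailed p < 0.1 is the criterion stated in the efficacy and sample-size text of both the synopsis and Section 12, and with 45 per arm it reproduces the 80% power.

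**Conclusion.** The concern holds. One-tailed p < 0.1 per dose gives a familywise error of 16.7% to 16.8%, not 20%, and a probability of declaring neither dose under the null of about 83%, not 80%. The 20% is the Bonferroni bound. Per-dose power of 80% is correct for 45 per arm. The at-least-one wording in the synopsis matches 80% only when one dose works; it is 91.3% when both do. Table 3 contradicts the planned 135 by 15 subjects (120).

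The figures assume equal evaluable numbers per arm and a common variance. Unequal dropout shifts the correlation a little, and the error stays between 16.1% and 17.3% for correlations of 0.6 to 0.4. They also precede any futility stopping. Section 12.2 says "A futility analysis may be conducted once at least 50 patients have completed their Day 27 assessments" but leaves the method to the SAP, so its effect cannot be computed here. The points should be corrected, but they do not threaten the validity of the trial.

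**What to change.** Keep the one-tailed p < 0.1 rule and make these changes before the SAP is finalized:

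1. **Section 12.1.5 and synopsis, efficacy:** replace the Dunnett 20% statement with either a familywise type 1 error of about 16.7%, or one of at most 20% (Bonferroni).
2. **Section 12.3 and synopsis, sample size:** give the probability of declaring neither dose when both true effects are zero as about 83%, before any futility stopping under Section 12.2.
3. **Same places:** use the per-dose definition of the 80% power. If an at-least-one figure is kept, give its scenario: 80% if one dose works, 91% if both do.
4. **Closing sentence of both:** call the null quantity the probability of declaring neither dose when both effects are zero, not power.
5. **Table 3:** reconcile the 40 per arm with 45.

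The cost is wording and one table; the criterion, the data collected and the 135 subjects stay as they are. If the sponsor instead confirms that a 20% Dunnett test was intended, the per-dose threshold becomes about 0.121. That would change the decision rule, not just the wording, and would have to be made explicitly before unblinding.

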12.2 Interim Analysis and Criteria for Early Termination

A futility analysis may be conducted once at least 50 patients have completed their Day 27 assessments. The focus of this unblinded analysis will be to assess the change from baseline in 2-day average OFF time at Day 27 as recorded in the Patient Motor Diary. Analysis of safety events and additional endpoints may be included. The analysis will be conducted by a biostatistician of the CRO who is not otherwise involved with the conduct of the study. Investigators, their study staff, patients, CRO team members, and the Sponsor will remain blinded. The outcomes of this analysis will include a recommendation to the Sponsor to:

- 1. Continue the study as planned; or
- 2. Discontinue randomization into one active treatment arm because of futility; or
- 3. Discontinue the study because of futility on both active treatment arms

The futility analysis will be described in the SAP.

12.3 Determination of Sample Size

The safety and tolerability of single- and repeated (7 daily) administration of CVN424, including doses higher than in the present study, were previously demonstrated in a study with 64 healthy volunteers. The target sample size of 45 subjects per treatment arm (total N=135) is considered to be sufficient for the preliminary evaluation of CVN424 safety, tolerability, and efficacy in a PD population. The study will have 90% power to detect at least one instance of any TEAE with an expected incidence of 0.10 per participant exposed at a given dosage of CVN424.

When the true effect of both dosages is zero, the study will have an 80% probability of declaring neither dosage of CVN424 significantly better than placebo at reducing OFF time based on the one-tailed p < 0.1 criterion, allowing 20% non-evaluable (e.g., loss to follow-up, incomplete data) and assuming a SD of 3 h for the change in OFF time from baseline to 27 days. When the true effect of a dosage is a reduction in average OFF time of at least 1.5 h, the study will have an 80% probability of declaring that dosage of CVN424 significant based on the one-tailed p < 0.1 criterion. By this construction, the study has 80% power to detect whether CVN424 does not reduce OFF time and

Study No. CVN424-201 Page 61 of 73

Protocol v. 4.0 14 July 2021

80% power to detect whether CVN424 at one or both of the two dosages tested reduces OFF time by at least 1.5 h.

Study No. CVN424-201 Page 62 of 73

Protocol v. 4.0 14 July 2021

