12.1.1 Analysis Sets

Safety Set

The Safety Analysis Set will consist of all subjects who enrolled and received at least 1 dose of study drug, classified according to the treatment they actually received. Subjects in this analysis set will be used for demographic, baseline characteristics and safety summaries.

Efficacy Set

The primary Efficacy Analysis set will consist of all subjects who were eligible, randomized, and received at least one dose of study drug, classified according to the treatment actually received. Secondary tests of efficacy will assess subjects who were eligible, randomized, and judged compliant with treatment and follow-up as classified prior to breaking the blind. The former is less stringent than a formal intent-to-treatment sample but estimates the efficacy one might expect among subjects who start using CVN424 at a specified dose, acknowledging that some will be intolerant or non-compliant. The latter estimates the maximal efficacy, the efficacy one might expect among subjects who are tolerant of and compliant with treatment. Subjects in this analysis set will be used for efficacy analyses.

PK Set

The PK set will consist of all subjects who received at least 1 dose of study drug and have at least 1 measurable plasma concentration. Subjects in this analysis set will be used for analysis of pharmacodynamics.

If any subjects are found to be noncompliant in dosing schedule or with incomplete data, a decision will be made on a case-by-case basis as to their inclusion in the analysis prior to breaking the blind, but they will be presented in the subject listings.

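### With 45 subjects per arm, the chance of seeing a TEAE of 10% incidence is 99%, not the stated 90%; 90% belongs to an incidence of 5%

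*Combined protocol and SAP*

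**What the plan says.** Section 12.3 sets the size of the trial: "The target sample size of 45 subjects per treatment arm (total N=135) is considered to be sufficient" for a preliminary look at safety, tolerability and efficacy. The next sentence gives the safety figure: "The study will have 90% power to detect at least one instance of any TEAE with an expected incidence of 0.10 per participant". It then ties that incidence to a single CVN424 dosage. The Sample Size Justification in section 2.0 (Study Summary) says the same.

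The sentence fixes everything the calculation needs: the criterion (one case or more), the incidence (0.10), the probability (90%) and the denominator (subjects exposed at one dosage, so a single active arm). Section 6.1 confirms equal arms: "subjects will be randomized in a 1:1:1 ratio into one of 3 study arms". Section 12.1.1 defines the Safety Set as "all subjects who enrolled and received at least 1 dose of study drug".

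The other calculations in section 12.3 concern OFF time. The rest of the safety justification is qualitative and refers to the earlier healthy-volunteer study.

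**The concern.** For a one-case-or-more criterion the probability is an elementary binomial result, and 90% looks too low for 45 subjects and a 10% event rate. The expected number of cases is 45 × 0.10 = 4.5, so an arm with none would be rare.

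Safety and tolerability is the primary objective (section 5.1.1), and the percentage of subjects with related TEAEs is the primary endpoint (section 5.2.1). This sentence is the only number linking the sample size to either. It tells the reader how rare an event can be and still be likely to appear in a dose arm, and hence what an arm with no cases would rule out. If the pair is wrong, a reader who relies on it will use the wrong detection limit. A reader could also conclude that 45 per arm is needed for a goal that about half that number would meet.

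**Working it through.** **Inputs**

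- Subjects per arm: n = 45 (section 12.3; section 2.0).
- Incidence: p = 0.10 per exposed participant (same sentence).
- Criterion: at least one case at one dosage (same sentence).
- Stated probability: 90%.
- Variants: 40 per arm (Table 3, section 8.1.3); 36 per arm, from 45 × 0.80, using the 20% non-evaluable allowance in section 12.3; 90 for both active arms pooled.

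**Attempt to reproduce the stated figure**

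P(at least one case) = 1 − (1 − p)^n

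1 − 0.90^45 = 0.9913, or 99.1%. The stated 90% is not reproduced.

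**Other readings, all at p = 0.10**

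| Reading | Probability |
|---|---|
| n = 45, one arm | 99.1% |
| n = 45, Poisson form 1 − exp(−4.5) | 98.9% |
| n = 45, each active arm shows at least one case (0.9913²) | 98.3% |
| n = 40 (Table 3) | 98.5% |
| n = 36 (45 less 20%) | 97.7% |
| n = 90 (both active arms) | 99.99% |

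None comes near 90%. The 36-per-arm reading is also hard to justify here, because the 20% allowance belongs to the OFF-time calculation and the Safety Set keeps everyone who took a dose.

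Changing the criterion to at least two subjects gives 88.7% (n = 36), 92.0% (n = 40) and 94.8% (n = 45). The text does not state that criterion, and at 45 it does not give 90% either.

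**Solving backwards**

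- Subjects needed for 90% at p = 0.10: ln(0.10) / ln(0.90) = 21.9, so 22.
- Incidence detectable with 90% probability, p = 1 − 0.10^(1/n): 0.0499 for n = 45; 0.056 for n = 40; 0.062 for n = 36; 0.025 for n = 90.
- Check at p = 0.05 and n = 45: 1 − 0.95^45 = 0.9006, or 90.06%.

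The pair that fits 45 per arm is therefore 90% with 0.05, almost exactly.

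**Is 90% meant as a floor?**

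The OFF-time power in the same section is a point value that reproduces. With 36 per arm, SD 3 h, effect 1.5 h and one-tailed 0.1, the standard error is 3 × √(2/36) = 0.707, and the power is Φ(1.5/0.707 − 1.282) = 80.0%, as stated. A reader will take the neighbouring 90% as a point value too.

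**The case against.** The arithmetic is not open to dispute; the objections concern consequence and remedy.

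- **The error is in the safe direction.** The plan understates what 45 per arm can detect. Read as a floor, the sentence is true. This stands, and it means that no participant is less protected and no sample size changes. But the text does not say that 90% is a minimum.
- **Nothing in the plan uses the figure.** The safety analysis consists of counts, percentages and listings by arm (section 12.1.4), and the stopping criteria are absolute case counts (section 6.3.1). No zero-count bound is planned, and an analyst who wanted one would compute it from the observed n. This also stands. The risk of a wrong detection limit is a risk to readers of section 12.3, not a step in the planned analysis.
- **The intended figure is unknown.** Either the 90% or the 0.10 may be the slip, and the documents do not show which. That is a reason to give both correct pairs.
- **The 0.05 pair has almost no margin.** One undosed subject in an arm gives 1 − 0.95^44 = 89.5%, and Table 3's 40 gives 87.2%. Enrolment is approximate, dosing starts after randomization, and the optional futility look (section 12.2) could stop one arm early. This is why the replacement must be conditional on 45 exposed. The 99% figure at 0.10 is far less sensitive: it is still 98.5% at 40.

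**Conclusion.** The sentence is wrong as written, in both places. With 45 exposed at a dosage, the probability of at least one case of a TEAE with 10% incidence is 99.1%, about 9 percentage points above the stated 90%. Put the other way, the incidence detectable with 90% probability is 0.050, half the stated 0.10.

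This rests on the criterion, incidence and denominator that the sentence itself gives, and on treating subjects as independent with a common incidence. It does not depend on which per-arm number is used, since 45, 40 and 36 all give more than 97%.

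The error understates the study's capability, so 45 per arm remains adequate and neither the design nor the analysis is affected. It should be corrected because it is the only quantitative sample-size support for the primary objective, and it cannot be reproduced.

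**What to change.** Replace the sentence in section 12.3 and in the Sample Size Justification of section 2.0 with, for example:

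> With 45 subjects exposed at a given dosage, the probability of observing one or more cases of a TEAE is 90% if its true incidence is 0.05 and 99% if its true incidence is 0.10.

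This is correct whichever figure was originally intended. Optionally, add that for both active arms pooled (n = 90) the incidence detectable with 90% probability is 0.025.

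While doing so, reconcile the 40 per arm in Table 3 with the 45 in section 12.3, because the 0.05 statement holds at 45 and not at 40.

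The cost is one sentence in two places and one table check, with no change to design, conduct or analysis.
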